Hg	Hemoglobin
HIPAA	Health Insurance Portability and Accountability Act
HIV	Human Immunodeficiency Virus
HRP	Horseradish peroxidase
HSF1	Health Sciences Facility building 1
ICF	Informed consent form
IDS	Investigational Drug Service

ICH	International Conference on Harmonization
IgA	Immunoglobulin A
IgG	Immunoglobulin G
IM	Intramuscular
IND	Investigational new drug
iNTS	Invasive non-typhoidal Salmonella
IP	Investigational product (a.k.a. study product)
IRB	Institutional Review Board
ISM	Independent safety monitor
IU	International units
KDO	2-keto-3-deoxyoctonate
LPS	Lipopolysaccharide
mcg or µg	Micrograms
mL	Milliliters
MOP	Manual of procedures
NTS	Non-typhoidal Salmonella
OPA	Opsonophagocytic activity
OPS	O polysaccharide
PBS	Phosphate buffered saline
pH	Potential of hydrogen
PBMC	Peripheral blood mononuclear cells
PI	Principal investigator
QA	Quality assurance
QC	Quality control
QMP	Quality management plan
S. (italicized S.)	Salmonella , bacteria of the genus
SAE	Serious adverse event
SBA	Serum bactericidal activity
SD	Standard deviation
SFC	Spot-forming cell
SMC	Safety monitoring committee
SOP	Standard operating procedure
TBIL	Total bilirubin
TLR5	Toll-like receptor 5
TT	Tetanus toxoid
U.S. or U.S.A.	United States (of America)
WBC	White blood cell
WHO	World Health Organization

PROTOCOL SYNOPSIS

Title:	Phase 1 Randomized, Placebo-Controlled, Dose-Escalation Study of the Safety, Reactogenicity, and Immunogenicity of a Trivalent (S. Enteritidis/S. Typhimurium/S. Typhi Vi) Conjugate Vaccine against Invasive Salmonella Disease Administered Parenterally to Healthy U.S. Adults
Phase:	1, adaptive design
Population:	104 healthy adults, ages 18 through 45
Site:	Two site, outpatient trial
Subject Participation Duration:	Each subject will participate for approximately 6-7 months from the time of enrollment through completion of the study.
Investigational Products:	
• Study product #1: trivalent S. Enteritidis [25 µg]/S. Typhimurium [25 µg]/S. Typhi Vi conjugate vaccine, presented in multi-dose vials containing 2-phenoxyethanol preservative.• Study product #2: placebo, a buffer containing the 2-phenoxyethanol preservative.
Primary Objectives:	
1. Safety and Reactogenicity: To assess the frequency and severity of solicited local (i.e., injective site) and systemic (such as fever) AEs during the first 7 days following each dose of vaccine.2. Safety: To assess the frequency and severity of unsolicited AEs within 28 days of each dose of vaccine and the occurrence of any SAEs through 6 months after the last dose of vaccine3. Immunogenicity: To measure the proportion of subjects that achieve a four-fold increase in titer, as compared to baseline, of specific serum IgG anti-COPS (S. Enteritidis or S. Typhimurium), anti-Vi (S. Typhi) polysaccharide, and anti-FliC (S. Enteritidis or S. Typhimurium) antibody at days 29 and 57, as measured by ELISA.
Secondary Objectives	
1. Safety: To assess the frequency and severity of abnormalities in clinical safety laboratory parameters at 7 days following the first dose of vaccine.2. Immunogenicity: To measure the proportion of subjects that achieve a four-fold increase in titer, as compared to baseline, of specific serum IgG anti-COPS (S. Enteritidis or S. Typhimurium), anti-Vi (S. Typhi) polysaccharide, and anti-FliC (S. Enteritidis or S. Typhimurium) antibody at day 180/210, as measured by ELISA.3. Immunogenicity: To calculate the GMT of serum IgG anti-COPS (S. Enteritidis or S. Typhimurium), anti-Vi polysaccharide, and anti-FliC (S. Enteritidis or S. Typhimurium) antibodies at days 1, 29, 57, and 180/210, as measured by ELISA.

Exploratory Objectives	
 1. Immunogenicity: To measure the titers of functional antibodies by serum bactericidal antibody (SBA) activity assay and opsonophagocytic activity (OPA) assay against S. Typhimurium, S. Enteritidis, and S. Typhi bacterial cells at days 1, 29, 57, and 180/210. 2. Immunogenicity: To measure the antibody secreting cells (ASC), specific for anti-COPS, Vi, FliC, and TT; possibly including homing markers and the measurement of antibodies in lymphocyte supernatants (ALS) 3. Immunogenicity: To measure memory B and T cells, specific for anti-COPS, anti-Vi, anti-FliC, and anti-TT activity; including the B cells that exhibit mucosal homing markers integrin $\alpha 4\beta 7$ and/or the lymph node homing marker CD62L 4. Immunogenicity: To conduct functional genomic and proteomic studies to further explore the immune response to vaccination. 5. Immunogenicity: To measure the anti-Vi polysaccharide, anti-TT, anti-COPS, and anti-FliC antibody levels in oral fluid at days 1, 29, 57, and 18/210, as measured by ELISA (Cohorts C and D)
-------------------------------	--

Brief Description of Study Design	
This is intended to be an adaptive design study.¹ In Part 1 of the study, we will conduct a double-blinded, randomized, placebo-controlled, dose-escalation study. Participants will be sequentially enrolled into Part 1 of the study in three dose-escalating steps (Steps 1-3, Cohorts A-C), consisting of fractional vaccine doses containing: 6.25 μg (Step 1), 12.5 μg (Step 2), or 25 μg (Step 3) of each specific polysaccharide by weight. Within each step, participants will be randomly allocated to receive a single dose of trivalent conjugate vaccine or placebo. In Step 3, participants may receive one dose or two-doses, separated by 28 days, of the vaccine.

--	---

Part 2 of the study is intended to expand the safety and immunogenicity data from a selected dose level of the vaccine (anticipated to be the 25 μ g per conjugate dose level). The target dose for this part of the study is to be informed by safety and immunogenicity data from the dose-escalation cohorts, with an intent to select the most promising immunogenic dose of the vaccine. Part 2 of the study will consist of a cohort of 60 participants who will be randomly allocated to receive a blinded two-dose regimen in one of the following three possible treatment groups:

- a single dose of the trivalent conjugate vaccine, followed by a dose of placebo 28 days later (n=25);
- two doses of trivalent conjugate vaccine, separated by 28 days (n=25);
- or two doses of placebo, separated by 28 days (n=10).

Special Notation: Due to the limited shelf-life of the vaccine, which is being determined by an ongoing stability testing plan, the availability of this pilot production lot of vaccine may be limited in time. Furthermore, since March 2020 the global pandemic due to SARS-CoV-2 virus (causing COVID-19 infections) has significantly disrupted the ability to conduct this study. Therefore, the Step 3 (Cohort C) has been significantly revised such that both a single and two-dose regimens of the 25 μ g dosage of vaccine will be evaluated, albeit with a very small sample size. This was originally intended to be evaluated with a large sample size in Part 2 (Cohort D), but due to the extraordinary present circumstances, the revised design of the study is intended to provide similar information which is crucial for the vaccine development plan. Furthermore, in order to provide some bridging immunogenicity data, a small number of participants in Cohort C will be randomized to receive either a single or two-dose regimen of

the 12.5 µg dosage of the vaccine. It is possible that Part 2 (Cohort D) will not be conducted, due to lack of vaccine.

Furthermore, because of the COVID-19 situation, for Cohort A the follow-up visits at 6 months post-vaccination were conducted by phone call contact and thus the collection of specimens was unable to be conducted. For Cohort B, the follow-up visits at 2 months and 6 months post-vaccination were conducted by phone call contact and thus the collection of specimens was unable to be conducted. Therefore for Cohort A and B participants, a single clinic visit for the collection of blood and oral fluid will be requested to measure the long-term immune responses (>6 months post-vaccination).

Pharmaron CPC, Inc. (Baltimore, MD) is being added as a site for the enrollment of Cohort C.

KEY PERSONNEL

Principal Investigator:

[name], MS, FACP, FIDSA
Professor of Medicine
Chief, Adult Clinical Studies section
Center for Vaccine Development & Global Health
University of Maryland School of Medicine
Direct Office [contact]
Mobile [contact]
Email: [contact]

Clinical Co-Principal Investigator:

[name], MB, ChB, FACP
Pharmaron CPC Inc.
[name]
Baltimore MD 21201
Office: [contact]

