Serological data demonstrate that a single dose of monovalent Typbar-TCV conjugate administered to Indian children 6-23 months of age is highly immunogenic in stimulating Vi antibodies and the titers remain elevated for up to 5 years post primary-immunization. There are no published or public human data to dictate the serum antibody response to a conjugate vaccine consisting of COPS conjugated to a carrier protein. Moreover, adult humans immunized with a glycoconjugate vaccine of any sort typically mount a maximal antibody response after the first dose that is not boosted following administration of a second dose of glycoconjugate. Therefore, the main purpose of administering two-sequential doses of trivalent conjugate separated by 4 weeks is to evaluate whether a two-dose regimen presents an increased risk for reactogenicity when the second dose is administered. A second dose is not expected to increase anti-COPS titers in U.S. adults but it may perhaps increase antibody avidity.

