2.2 Work flow of the Phase 1 study in U.S. adults

Eligible subjects will be screened, enrolled, and vaccinated at the CVD Outpatient Vaccine Clinic (located on the 4th floor of HSF1) or Pharmaron (located in the UMB BioPark 1 building). After the documentation of informed consent, subjects will be screened for eligibility; eligible subjects will subsequently be enrolled and randomized to a treatment group. On Day 1 (and Day 29, for participants in Cohorts C and D), study product will be administered, in double-blinded fashion, as an intramuscular injection into the deltoid muscle. Following vaccination, there will be a 20-minute post-vaccination observation period. Following each dose of study product, safety and reactogenicity will be measured by a daily oral temperature and solicited AE reporting over the subsequent 7 days (via a 7-day memory aid); unsolicited AE reporting will occur through 28 days following the last dose of vaccine. The occurrence of any SAEs will be recorded through 6 months after the last dose of vaccine (Day 180 or 210, for participants in Cohort C and D).

Subjects in Steps 1-2 (Cohorts A-B) will complete four additional outpatient visits on Days 8, 29, 57, and 180 (final visit). Subjects in Cohorts C and D will complete five additional outpatient visits on Days 8, 29 (second dose of masked study product), 36, 57, and 210 (final visit). The recording of AEs and concomitant medication change information, the performance of a physical exam (if indicated), and the collection of study-specific samples will be performed during these outpatient visits. Clinical safety laboratory tests will be evaluated on Day 8. The final study visit will be for the collection of SAE information (Day 180 or 210).

After the completion of enrollment of each cohort, the safety data through 7-days post-vaccination are to be reviewed by an independent Safety Monitoring Committee (SMC). The SMC must provide approval prior to the enrollment of the subsequent dose-escalating cohort. Immunology data may not be available at the times of these scheduled SMC reviews.

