In addition to the evaluation of safety, immunogenicity assessments are planned to evaluate the immune responses induced by the three different vaccine formulations. The study, however, is not statistically powered to determine significance of any pre-specified difference. Therefore, there was no formal sample size calculation, based on immunogenicity, as the basis for the designed study. Nonetheless, the sample size was chosen based on the number of subjects appropriate for a phase 1 study in which these vaccines have never been evaluated in humans.

[figure not shown]
Schematic of Study Cohorts

Cohort	Vaccine	Dose of each COPS and of Vi (µg)	No. Subjects	Dose #1	Dose #2	Vaccination Days
A (Step 1)	Trivalent Placebo	6.25 0	8 2	Vaccine Placebo	- -	1
SMC review of available safety data through 7-days post-vaccination before proceeding to the next dosage cohort						
B (Step 2)	Trivalent Placebo	12.5 0	10 2	Vaccine Placebo	- -	1
SMC review of available safety data through 7-days post-vaccination before proceeding to the next dosage cohort						
C (Step 3)	Trivalent	25	6	Vaccine	Vaccine	1& 29*
	Trivalent	25	6	Vaccine	Placebo	1 & (29)*
	Trivalent	12.5	4	Vaccine	Vaccine	1& 29*
	Trivalent	12.5	4	Vaccine	Placebo	1 & (29)*
	Placebo	0	2	Placebo	Placebo	1 & (29)*
SMC review of available safety data through 7-days post-vaccination before proceeding to Part 2 of the study						
D (Expanded, confirmatory cohort)	Trivalent	(highest, well-tolerated dose among cohorts A-C)	25	Vaccine	Vaccine	1 & 29*
	Trivalent		25	Vaccine	Placebo	1 & (29)*
	Placebo		10	Placebo	Placebo	1 & (29)*
Total			N = 104			

* In cohorts C and D, the trivalent vaccine will be administered as a single dose (day 1) or as a two-dose (days 1 and 29) regimen. In order to maintain the masking of study products, on day 29 a placebo will be administered when indicated by the parentheses.

SMC, Safety Monitoring Committee

Schematic of the Flow of the Cohort enrollments and timing of SMC meetings:

Cohort D

Trivalent on day 1, (placebo on day 29);
Trivalent on day 1 and day 29;
Or Placebo on day 1 and day 29

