6.4 Visit 3 Follow Up (Day 8 ±1)

The participant will return to clinic to complete the following:

- Interim medical history or concomitant medications
- A targeted physical examination, if indicated based on review of interim medical history
- Collection and review of the *Memory Aid* for reactogenicity information and completion of the corresponding source document.
- Any other unsolicited adverse events (AEs) will be recorded
- A blood volume 12.5 mL for safety laboratory assessment, consisting of:
 - Hematology (4 mL, lavender, EDTA tube): total WBC, ANC, Hg, platelets
 - Chemistries (8.5 mL, red, serum separator tube): creatinine, AST, ALT, TBIL, CRP
- A blood volume of 40 mL for PBMC (for Cohorts B, C, and D only)
- If available, the result from the PCR testing performed on Day 1 will be provided to the participant
- Prior to discharge, a reminder of the date and time for the next visit will be given to the participant

6.5 Visit 4 Follow Up (for Cohorts A-B) or Vaccination Dose #2 (for Cohorts C and D) (Day 29 ±3)

The participant will return to clinic to complete the following, prior to vaccination:

- Interim medical history or concomitant medications

- A targeted physical examination, if indicated based on review of interim medical history
- Collection of any AEs will be recorded
- A blood volume of 20 mL for serum and 80 mL for PBMC
 - 5 mL for a SARS-CoV-2 antibody test, to be performed at University of Maryland Pathology Associates (UMPA)
- Collect nasopharyngeal swab for SARS-CoV-2 PCR test, to be performed at University of Maryland Pathology Associates (UMPA)
- Collect oral fluid (crevicular fluid)
- For women of child-bearing potential, a urine pregnancy will be performed (for Cohort C and D only)
- Confirmation of eligibility for dose #2, if Cohort C and D

For Cohort C and D, the unblinded vaccinator and unblinded checker will administer the appropriate study product and record the procedure on the respective source document. Following receipt of vaccine, the participant will be directly observed for at least 20 minutes and given instructions on the completion of a *Memory Aid*. Prior to discharge, follow-up visit information and contact numbers will be provided.

6.6 Visit 5 Follow Up, only for Cohort C and D (Day 36 ±1)

The participant will return to clinic to complete the following:

- Interim medical history or concomitant medications
- A targeted physical examination, if indicated based on review of interim medical history

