7.3 Halting Rules

If any of the following halting rules are met, the study will not proceed with the remaining enrollment or dose escalation without a review by and recommendation from an Independent Safety Monitoring Committee:

- Two or more subjects in a dosage cohort experiences the same systemic toxicity, except for fever, of grade 3 or above and judged to be associated with vaccine.
- Two or more subjects in a dosage cohort experiences a fever at or greater than grade 3 within 7 days of vaccination.
- Two or more subjects in a dosage cohort experiences the same grade 2 or greater abnormal laboratory value and judged to be associated with vaccine.
- Three or more subjects in a dosage cohort experience the same localized toxicity (local pain or induration) at grade 3 or above judged to be associated with vaccine.
- Any death occurring within 7 days following administration of vaccine that was not the result of trauma or accident.
- Any subject experiences an SAE determined to be related to vaccine.

The study may also be halted due to PI or Sponsor discretion.

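### As worded, a met halting rule suspends enrollment and dose escalation but not the Day 29 second doses given in Cohort C

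*Combined protocol and SAP*

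**What the plan says.** **Second doses.** The Special Notation in the Protocol Synopsis states that "Step 3 (Cohort C) has been significantly revised such that both a single and two-dose regimens of" the 25 mcg dosage are evaluated. Section 2 and the cohort table in Section 2.2 give six Cohort C participants 25 mcg on Days 1 and 29, and four participants 12.5 mcg on both days. The other twelve receive placebo on Day 29 to keep the mask. Section 2.1 states that the main purpose of two sequential doses "is to evaluate whether a two-dose regimen presents an increased risk for reactogenicity when the second dose is administered".

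**Halting.** Under Section 7.3, once a rule is met "the study will not proceed with the remaining enrollment or dose escalation without a review" and recommendation by the SMC. The triggers include two or more subjects with "the same grade 2 or greater abnormal laboratory value and judged to be associated with vaccine", grade 3 systemic or local reactions, grade 3 fever, related SAEs and certain deaths. A closing sentence lets the PI or sponsor halt the study at their discretion.

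**Scheduled review.** Section 2.2 says: "After the completion of enrollment of each cohort, the safety data through 7-days post-vaccination are to be reviewed" by the SMC, whose approval is needed before the next dose-escalating cohort enrolls. The Cohort C row of the table reads "SMC review of available safety data through 7-days post-vaccination before proceeding to Part 2 of the study". Section 7.4 limits the reviewed data to the first 7 days after the first dose. Of Part 2, the Special Notation says: "It is possible that Part 2 (Cohort D) will not be conducted, due to lack of vaccine".

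**Before dose 2.** Section 6.5 requires "Confirmation of eligibility for dose #2, if Cohort C and D". Exclusion criteria 2 and 5 in Section 3.2 apply laboratory limits and an acute-illness check to that visit.

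**The concern.** The Special Notation explains that the two-dose comparison was first meant for Part 2, where it would have followed the SMC's review of Cohort C. Once second doses are given inside Cohort C, participants can be redosed without a cohort boundary being crossed. The halting consequence in Section 7.3 is written in terms of enrolling new people and moving to a higher dose. Repeating a dose in someone already enrolled is neither.

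What is at stake is the case the rules exist for: a signal appears after first doses at the highest level, a rule is met, and the protocol does not tell staff to hold the next injection. Section 1.5.1 calls the risks of this first-in-human vaccine unknown, and Section 2 says the escalating cohorts were enlarged to detect reactogenicity from flagellin.

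**Working it through.** **1. Doses affected (Section 2).** Cohort C is 6 + 4 + 6 + 4 + 2 = 22. With Cohorts A (10) and B (12) this reproduces the stated 44 for Part 1; adding Cohort D (60) gives the stated 104. First 25 mcg doses: 6 + 6 = 12. Second vaccine doses: 6 at 25 mcg + 4 at 12.5 mcg = 10.

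**2. What a met rule holds.**

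| Activity after a rule is met on first-dose data | Named in Section 7.3? |
|---|---|
| Remaining Cohort C enrollment | Yes |
| Cohort D enrollment (up to 60) | Yes, as remaining study enrollment |
| Move to a higher dose | Yes, though 25 mcg is the top level |
| Day 29 second doses in enrolled participants (up to 10) | No |

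An example: suppose two participants have vaccine-related C-reactive protein of grade 2. Appendices B and C put that threshold at 2.0 × 0.8 = 1.6 mg/dL. The laboratory rule is met. Those two also exceed the eligibility limit of 1.1 mg/dL and would fail their own dose 2 check, unless the single permitted repeat is acceptable. The others due a second dose pass their own checks, and nothing in Section 7.3 holds their injections. Section 5.2 schedules post-vaccination safety laboratory tests only on Days 2 and 8, so scheduled results bearing on the laboratory rule all come from first doses.

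**3. Chance that a two-subject rule is met on first 25 mcg doses.** The rates of a qualifying event are assumed. The nearest figure in the documents is 1% to under 10% for fever, pain and swelling with the licensed Vi component (Section 1.4), which has no flagellin carrier. P(X ≥ 2) with n = 12:

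| Assumed rate | 5% | 10% | 20% | 30% |
|---|---|---|---|---|
| P(2 or more of 12) | 0.12 | 0.34 | 0.73 | 0.92 |

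The eight first 12.5 mcg doses in the same cohort are left out.

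**4. Timing of the scheduled review.** Let E be the days from first to last Cohort C enrollment, which the legible text does not state. The first Day 29 injection falls 28 days after the first dose 1. A review holding the last enrollee's 7-day data precedes it if E + 7 ≤ 28, so E ≤ 21. At the early edge of the window the limit is 25 − 7 = 18 days, or 25 − 8 = 17 if the Day 8 visit is also a day late. No review lag is allowed for.

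Assuming even enrollment, and a review on day R:
- second 25 mcg doses given before it = 6 × max(0, (R − 28)/E), with R = E (available data) or R = E + 7 (complete 7-day data);
- first 25 mcg doses with 7-day data at the first Day 29 visit = 12 × min(1, 21/E);
- Cohort C places still open at that visit = 22 × max(0, 1 − 28/E).

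| E (days) | Redosed at 25 mcg, R = E | Redosed at 25 mcg, R = E + 7 | First doses with 7-day data | Cohort C places open |
|---|---|---|---|---|
| 21 | 0 | 0 | 12 | 0 |
| 30 | 0.4 | 1.8 | 8.4 | 1.5 |
| 42 | 2.0 | 3.0 | 6.0 | 7.3 |
| 60 | 3.2 | 3.9 | 4.2 | 11.7 |

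A simulation of 20,000 runs with random accrual and the ±3-day window gives 0.5–1.8, 2.0–3.0 and 3.2–3.9 redosed for E = 30, 42 and 60. Any Cohort D enrollment is additional to the last column.

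**The case against.** The best defense is that nobody would redose after a halting rule was met. The section is about halting, and its last sentence says the PI or sponsor may *also* halt the study, which suggests that a met rule already does so. Any met rule brings in the SMC. The ISM reviews SAEs in real time (Section 7.4), each participant is rechecked before dose 2, and a new clinical finding allows withdrawal (Section 3.4). A two-dose 25 mcg Vi conjugate regimen was well tolerated in children, and rabbits tolerated four doses of the trivalent product (Sections 1.4 and 1.3.2). All of this lowers the practical risk. It does not change the stated scope: one word in the discretion sentence does not widen an explicit list, discretion is not a rule, and individual checks do not pool events across participants.

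Three stronger readings are tempting, and the documents do not support them:
- *That the rules ignore events after dose 2.* The triggers refer to vaccination without a dose number, so such events count. Only the consequence is too narrow.
- *That once Cohort C is full a met rule has nothing left to suspend.* Up to 60 Cohort D enrollments may remain; the Synopsis says only that Part 2 might not run.
- *That 25 mcg first-dose data go unreviewed before redosing.* A review is scheduled, and whether it comes in time depends on enrollment pace. The Section 2.2 schematic of SMC meeting timing is missing from the text reviewed and may settle the matter. Section 7.4's reference to post-first-dose data is consistent with a look before dose 2, though it does not establish one.

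**Conclusion.** The concern holds for the consequence clause of Section 7.3. A halting rule met on Cohort C first-dose data would, as written, stop new enrollment and escalation while leaving up to ten second doses, six of them at 25 mcg, free to proceed unless someone used discretion. That conclusion needs no assumption about enrollment. How often it would matter depends on event rates the documents do not give.

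The timing of the scheduled SMC review is a secondary, conditional point. The legible text ties it to completed enrollment and to Part 2, not to Day 29. Under the assumed enrollment spans, the number redosed at 25 mcg before that review runs from 0 of 6 (21 days or less) to between 3.2 and 3.9 of 6 (60 days). If the schematic already places the review before Day 29, only the text needs aligning.

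**What to change.** **Main change.** In Section 7.3, list second doses with remaining enrollment and dose escalation among the activities that may not proceed without SMC review and recommendation. The cost is wording. The operational downside is that a halt may push some Day 29 injections outside the ±3-day window. Because Day 29 is masked, a hold would in practice affect every arm and could shift the Day 29 and Day 57 samples, which are primary immunogenicity timepoints. Section 6.5 collects the Day 29 blood before the injection, so the protocol could have that sample taken on schedule while only the injection waits.

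**Conditional change.** Check the Section 2.2 schematic. If it does not already do so, state in Sections 2.2 and 7.4 and in the Cohort C row of the table that the SMC sees the available 7-day first-dose Cohort C data before the first Day 29 injection. With enrollment of about 21 days or less and no review lag (17 to 18 days at the early edge of the window), the scheduled meeting serves. With slower enrollment it means one short extra look and amending the count of three scheduled meetings in Section 7.4. That look would be limited: with 7-day data on 4 to 8 recipients, the chance of seeing two or more events is 0.05 to 0.19 at an assumed 10% rate and 0.35 to 0.75 at 30%. It should inform SMC judgment and not act as an automatic stop.
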